24.6 Clinical Efficacy Analysis

24.6.1 ACR CRISS (American College of Rheumatology Composite Response Index for clinical trials in early diffuse cutaneous Systemic Sclerosis)

ACR CRISS incorporates multisystem involvement in diffuse cutaneous systemic sclerosis/scleroderma and includes the patient's perspective and the impact of the disease on functional disability (17.3.6 Description of Study Measures, ACR CRISS).

The ACR CRISS is calculated as a 2-step process. The four individual possible outcomes of Step 1 ACR CRISS which include new scleroderma renal crisis, decline in % predicted $\geq 15\%$ (relative), new decline of left ventricular ejection fraction to 45% or less attributable to scleroderma, and new onset pulmonary arterial hypertension attributable to scleroderma will be tabulated and summarized descriptively for both treatment groups at study Day 1, study day 84 (week 12) and study day 168 (week 24).

Step 2 ACR CRISS calculates changes from baseline in the predicted probability of improvement and will be applied and summarized descriptively for both treatment groups at study day 84 (week 12) and study day 168 (week 24).

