- New onset of pulmonary arterial hypertension attributable to SSc that requires treatment (pulmonary arterial hypertension is defined as mean pulmonary artery pressure ≥ 25 mmHg at rest, an end-expiratory pulmonary wedge pressure ≤ 15 mmHg, and a pulmonary vascular resistance > 3 Wood units).

If any one of these is present, the participant is classified as not improved regardless of changes in other parameters.

The second step assesses participants and calculates the predicted probability of improvement based on changes in the mRSS, FVC % predicted, patient global assessment, physician global assessment, and HAQ-DI.

ACR CRISS will be applied study Day 1 (using FVC % predicted at screening within 21 days), study day 84 (week 12) and study day 168 (week 24). For the extension study ACR CRISS will be applied study day 84 (week 36) and study day 168 (week 48).

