24.6.2 Additional Assessments for Clinical Efficacy

Analysis of these additional efficacy assessments will be based on the safety population. Clinical efficacy assessments will include each of the individual components of ACR CRISS as follows:

- mRSS (modified Rodnan skin score)
- FVC % predicted
- HAQ-DI (Health Assessment Questionnaire-Disability Index)
- PtGA (Patient Global
- MDGA (Physician Global Assessment)

Additional clinical efficacy measures include:

- DLCO % predicted
- HRCT chest scan ILD severity using the Goh scoring method
- Patient reported outcome Mahler Baseline/Transitional Dyspnea Index (Mahler BDI/TDI).

The results of mRSS score and changes from baseline at study day 84 (week 12) and study day 168 (week 24) will be summarized without imputation for missing values.

The percent predicted FVC and DLCO results and change from screening at study day 28 (week 4), day 56 (week 8), day 84 (week 12), day 112 (week 16), day 140 (week 20) and study day 168 (week 24) will be summarized descriptively without imputation for missing values. Total lung capacity results and change from screening at study day 84 (week 12) and study day 168 (week 24) will be summarized descriptively without imputation for missing values.

HRCT chest scan Goh scoring of ILD severity and change from baseline at study day 168 (week 24) will be summarized descriptively.

The results for each of the disease-status scales Mahler BDI/TDI, SHAQ, PtGA and MDGA and changes from baseline at study day 84 (week 12) and study day 168 (week 24) will be summarized descriptively without imputation for missing values.

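### CRISS Step 2 is planned as a change from baseline although it has no baseline value, Step 1 failures are not carried into its summary, and BDI/TDI lacks a like-for-like baseline

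*Combined protocol and SAP*

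**What the plan says.** **Definition (17.3.6).** CRISS has two steps. Step 1 lists four events that may develop after treatment: renal crisis, a confirmed relative fall in FVC % predicted of at least 15%, a fall in ejection fraction, and new pulmonary arterial hypertension. The rule is: "If any one of these is present, the participant is classified as not improved regardless of changes in other parameters". Step 2 then "calculates the predicted probability of improvement based on changes in the mRSS" and four other components: FVC % predicted, the patient and physician global assessments, and HAQ-DI. The section also says that CRISS is applied on Day 1, with the screening FVC.

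**Analysis (24.6.1).** The section refers back to "17.3.6 Description of Study Measures, ACR CRISS". It tabulates the four Step 1 outcomes by group at Day 1, week 12 and week 24. For the second step it says "Step 2 ACR CRISS calculates changes from baseline in the predicted probability of improvement", summarised by group at weeks 12 and 24. Sections 24.8.1, 25.5.2.1 and 25.5.4.1 describe Step 2 in the same way for the post-discontinuation and extension analyses.

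**Dyspnea (24.6.2).** The planned summary is "The results for each of the disease-status scales Mahler BDI/TDI, SHAQ, PtGA and MDGA and changes from baseline" at weeks 12 and 24. Section 25.5.2.2 extends this to weeks 36 and 48. In the visit lists, Day 1 (18.3.1) has the Mahler BDI. Weeks 12 and 24 (18.3.7, 18.3.10) and weeks 36 and 48 (25.2.4, 25.2.7) have the Mahler TDI.

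**The concern.** CRISS is the first-listed measure under the secondary objective (6.2). Taken literally, its analysis sections ask for a difference between a post-baseline probability and a baseline probability that does not exist. Two programmers could produce different tables: one might report the probability, another might subtract some constant assigned to Day 1.

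Separately, the analysis sections do not turn the Step 1 override into a number. A participant with a Step 1 event could enter the Step 2 summary with the raw probability, enter as not improved, or be left out. Three of the four Step 1 events are not Step 2 components, so a participant can fail Step 1 and still have a favourable raw Step 2 value.

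The dyspnea index raises a similar question, because no instrument is measured both at Day 1 and later.

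**Working it through.** The plan gives no figure for CRISS (no expected level, event rate or responder cut-off), so there is nothing to reproduce. The check compares the text and then illustrates the size.

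**Step 2.**
- 17.3.6: the inputs are changes in five components, and the output is one probability per participant per post-baseline visit. At Day 1 every change is undefined or zero by construction, so no informative probability exists there.
- 24.6.1, 24.8.1, 25.5.2.1, 25.5.4.1: the output is a change from baseline in that probability.
- These cannot both be right. Applying CRISS on Day 1 (17.3.6) and tabulating Step 1 on Day 1 (24.6.1, 25.5.2.1) add to the confusion, since Step 1 events are defined as developing after treatment.

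**Step 1.** 17.3.6 has the override and 24.6.1 cites that section. No analysis section states the value a failure takes in the Step 2 summary or defines a combined result. Omission is a practical possibility: a sustained fall in FVC attributed to worsening ILD can lead to discontinuation (15.0), and that participant may then be followed under 24.8.1, which has the same gap.

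**Size for the mean.** Let n be the group size, k the Step 1 failures, m the mean Step 2 probability in the others, and q the failures' mean raw probability.
- Failures counted as 0: (n − k)m/n
- Raw values used: ((n − k)m + kq)/n, which is higher by kq/n
- Failures left out: m, which is higher by km/n

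The planned n is 6 per group and 12 in total (7.1). The ranges q = 0 to 0.5 and m = 0.3 to 0.7 are assumptions; the documents give neither.

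| n | k | Raw values used (kq/n) | Failures left out (km/n) |
|---|---|---|---|
| 6 | 0 | 0 | 0 |
| 6 | 1 | 0 to 0.083 | 0.050 to 0.117 |
| 6 | 2 | 0 to 0.167 | 0.100 to 0.233 |
| 12 | 1 | 0 to 0.042 | 0.025 to 0.058 |

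Example with n = 6, k = 1, m = 0.5, q = 0.2: counted as 0, 5 × 0.5/6 = 0.417; raw, (2.5 + 0.2)/6 = 0.450; left out, 0.500.

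**Chance that it arises.** With an assumed Step 1 event rate p per participant, the chance of at least one failure is 1 − (1 − p)^n.

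| p | n = 6 | n = 12 |
|---|---|---|
| 2% | 0.114 | 0.215 |
| 5% | 0.265 | 0.460 |
| 10% | 0.469 | 0.718 |
| 20% | 0.738 | 0.931 |

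**BDI/TDI.** A change from Day 1 would pair a BDI with a later TDI, which are different instruments. Section 17.3.3 gives no scoring. That TDI is itself a transition score is inferred from its name and from the schedule; the mismatch between instruments is explicit.

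**The case against.** The strongest reply is that the plan is usable as it stands. The override is written in 17.3.6, and 24.6.1 points there. Step 2 is summarised only after baseline, so the sentence can be read as loose wording for a probability computed from changes. Step 1 events have their own table, so failures stay visible. Efficacy is secondary and no hypothesis is tested (24.2).

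Much of this stands, and it limits the point. A reader might infer that the plan will mix Step 1 failures with improvers and so report too favourable a result. The documents do not say that: they are silent on the coding, and a bias needs both a Step 1 failure and an analyst who uses the raw value or omits the participant. A reader might also pick a high raw value such as 0.9, giving 0.9/6 = 0.15. No document value supports it, and a participant who failed on FVC has worsened on a Step 2 component.

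Nor are the efficacy outputs undefined in general. mRSS, FVC, DLCO, total lung capacity, SHAQ, PtGA, MDGA and the Goh score have ordinary change summaries. The dyspnea point does not extend to 24.8.2: change there is taken from the early-discontinuation visit, which follows the week 24 list and collects TDI, so a same-instrument reference exists.

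The reply does not remove the contradiction between four analysis sections and the definition they rely on. A general cross-reference also does not tell a programmer what number a Step 1 failure receives.

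**Conclusion.** The point holds in three limited parts. The Step 2 wording in 24.6.1, 24.8.1, 25.5.2.1 and 25.5.4.1 contradicts 17.3.6. Those sections do not carry the Step 1 override into the Step 2 summary. In 24.6.2 and 25.5.2.2 only, the planned change from baseline in BDI/TDI has no same-instrument baseline.

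The consequence is confined to CRISS and BDI/TDI, which are secondary and descriptive. The numerical effect depends on the assumed q and m and on scoring not improved as 0, which is a proposed coding and not a value in the documents. On that basis, one failure in a group of 6 moves the mean by at most about 0.08 (raw value) or 0.12 (left out). Without a Step 1 failure only the wording conflict remains. It should be corrected before the tables are programmed.

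**What to change.** 1. In 24.6.1, 24.8.1, 25.5.2.1 and 25.5.4.1, state that Step 2 yields a predicted probability computed from component changes from baseline, and summarise that probability at each post-baseline visit with no subtraction.
2. In the same sections, add one combined CRISS result in which any participant with a Step 1 event is carried as not improved (for example probability 0). Keep the separate Step 1 table.
3. Drop the Day 1 application of CRISS in 17.3.6 and the Day 1 Step 1 tabulation in 24.6.1 and 25.5.2.1. The baseline component values are still needed.
4. In 24.6.2 and 25.5.2.2, report BDI at Day 1 and TDI as scored at later visits, without subtracting a Day 1 value. Leave the reference point in 24.8.2 as it is.

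The cost is SAP wording only: no new data and no change to visits. The one downside is that the CRISS summary may become slightly less favourable if a Step 1 event occurs.

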24.6.2 Additional Assessments for Clinical Efficacy

Analysis of these additional efficacy assessments will be based on the safety population. Clinical efficacy assessments will include each of the individual components of ACR CRISS as follows:

- mRSS (modified Rodnan skin score)
- FVC % predicted
- HAQ-DI (Health Assessment Questionnaire-Disability Index)
- PtGA (Patient Global
- MDGA (Physician Global Assessment)

Additional clinical efficacy measures include:

- DLCO % predicted
- HRCT chest scan ILD severity using the Goh scoring method
- Patient reported outcome Mahler Baseline/Transitional Dyspnea Index (Mahler BDI/TDI).

The results of mRSS score and changes from baseline at study day 84 (week 12) and study day 168 (week 24) will be summarized without imputation for missing values.

The percent predicted FVC and DLCO results and change from screening at study day 28 (week 4), day 56 (week 8), day 84 (week 12), day 112 (week 16), day 140 (week 20) and study day 168 (week 24) will be summarized descriptively without imputation for missing values. Total lung capacity results and change from screening at study day 84 (week 12) and study day 168 (week 24) will be summarized descriptively without imputation for missing values.

HRCT chest scan Goh scoring of ILD severity and change from baseline at study day 168 (week 24) will be summarized descriptively.

The results for each of the disease-status scales Mahler BDI/TDI, SHAQ, PtGA and MDGA and changes from baseline at study day 84 (week 12) and study day 168 (week 24) will be summarized descriptively without imputation for missing values.

24.7 Post-Discontinuation Assessments for Safety

Participants who prematurely and permanently discontinue ixazomib study medication and continue with post-discontinuation monitoring visits will be used for the analysis of post-discontinuation safety data. Summaries of AEs, deaths, and patient disposition will be presented.

Safety outcome measures used will include, but will not be limited to:

- Treatment-emergent (not ixazomib) AEs
- Treatment-emergent (not ixazomib) SAEs
- Treatment-emergent (not ixazomib) treatment-related AEs
- Treatment-emergent (not ixazomib) treatment-related SAEs
- Treatment-emergent (not ixazomib) changes in clinical laboratory measures
- Treatment emergent (not ixazomib) changes in patient vital signs
- Treatment emergent (not ixazomib) changes in UCLA SCTC GIT 2.0 questionnaire

24.8 Post-Discontinuation Clinical Efficacy Analysis

Participants who prematurely and permanently discontinue ixazomib study medication and continue monitoring with post-discontinuation visits will be used for the analysis of post-discontinuation clinical efficacy data.

24.8.1 Post-Discontinuation ACR CRISS (American College of Rheumatology Composite Response Index for clinical trials in early diffuse cutaneous systemic Sclerosis)

ACR CRISS incorporates multisystem involvement in diffuse cutaneous systemic

sclerosis/scleroderma and includes the patient's perspective and the impact of the disease on functional disability (17.3.6 Description of Study Measures, ACR CRISS).

The ACR CRISS is calculated as a 2-step process. The four individual possible outcomes of Step 1 ACR CRISS which include new scleroderma renal crisis, decline in FVC % predicted \geq 15% (relative), new decline of left ventricular ejection fraction to 45% or less attributable to scleroderma, and new onset pulmonary arterial hypertension attributable to scleroderma will be tabulated and summarized descriptively for post-discontinuation visit 3 (PD day 84 \pm 4 days) as required and the final post-discontinuation visit.

Step 2 ACR CRISS calculates changes from baseline in the predicted probability of improvement and will be applied and summarized descriptively for post-discontinuation visit 3 (PD day 84 \pm 4 days) as required and the final post-discontinuation visit.

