7.0 STUDY DESIGN

7.1 Overview

This is a phase 2 open-label, safety and tolerability pilot study of oral ixazomib in patients with scleroderma-ILD (SSc-ILD). Planned enrollment will be 12 patients who have been seen in the Mayo Clinic Arizona Scleroderma program among whom will be 6 participants already taking SSc-ILD background medication mycophenolate (MMF) at stable dose for at least 3 months, and 6 participants who either have not taken a SSc-ILD background medication within 3 months of study screening or by the time of study screening will complete medication washout of medications being taken for SSc-ILD other than MMF. The number of study candidates needing to washout medications other than MMF is anticipated to be very low based on the low prevalence of medicines other than MMF used clinically for the treatment of scleroderma-ILD. No study candidate already taking MMF will be asked to wash out MMF. Eligible participants include male and female adult patients at least 18 years of age, fulfilling the 2013 American College of Rheumatology (ACR)/European League Against Rheumatism (EULAR) criteria for systemic sclerosis/scleroderma [151] and having disease duration \leq 60 months based on first non-Raynaud's phenomenon manifestation. ILD is based on features observed from the participant's HRCT chest scan obtained within 3 months prior to either medication washout or screening visit, as applicable. Studyscreening

will include pulmonary function testing demonstrating FVC \geq 45% predicted and DLCO \geq 40% predicted, which will also be determined to be stable measurements as compared with previous pulmonary function testing obtained clinically within the prior 3-12 months. For the 6 study participants who are taking stable dose background MMF, the MMF will be continued at the same dose during the study. MMF will be prescribed as routine clinical care and will not be provided as part of the study. All 12 participants will be administered oral ixazomib. Ixazomib dose modification or interruption will be allowed for safety or tolerability reasons at any time during the study. Any patient who permanently and prematurely discontinues study treatment will also be discontinued from the study.

There are four study periods (all durations are in calendar days):

- **Washout Period:** \leq 90 days:
 - **Participants who are taking background SSc-ILD medication other than MMF at screening:**

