7.2 Rationale for Study Design

This is an open-label safety and tolerability pilot study of oral ixazomib in patients with SSc-ILD. An ixazomib dose of 4 mg orally on days 1, 8, and 15 of a 28-day treatment cycle for 6

cycles will be evaluated. This dose is approved for the treatment of multiple myeloma in combination with lenalidomide and dexamethasone in patients who have received at least 1 prior therapy [143].

A six cycle treatment duration was chosen in light of the improved safety profile of oral ixazomib over the earlier proteasome inhibitors bortezomib given either intravenously or subcutaneously and carfilzomib given intravenously particularly in regard to the potential adverse effect of peripheral neuropathy. The common and expected adverse effects have been shown to manifest most often in the initial months of treatment.

To accommodate current approaches to the treatment of SSc-ILD, the study will include 6 study participants taking a stable oral dose of MMF for at least 3 months with ixazomib added to their ongoing treatment, and 6 study participants not receiving treatment specifically for SSc-ILD at study screening. The maximum dose MMF (≤ 1.5 g BID) in this study is based on the dose most frequently used in patients with SSc-ILD. This is the same dose used in the randomized, double-blind, controlled Scleroderma Lung Study-II (SLS II) study comparing oral cyclophosphamide for 1 year plus 1 year placebo with MMF for two years [152].

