15.0 EARLY DISCONTINUATION

Patients will be free to discontinue their participation in the study at any time and without prejudice to further treatment. In addition, patients will permanently discontinue study

drug and will be discontinued from study for any of the following reasons:

- Unacceptable toxicity
- Interruption of study treatment for >28 days because of an AE(s)
- Patients who were on no background SSc-ILD medication at study entry and need to begin a SSc-ILD medication:
 - A decline of FVC by $\geq 15\%$ predicted or a decline of DLCO by $\geq 15\%$ predicted observed during the study that is sustained 4 weeks, or a decline of FVC itself to $<45\%$ predicted or decline of DLCO itself to $<40\%$ predicted observed during the study and if not explained by alternative etiology other than worsening scleroderma-related ILD as confirmed by HRCT chest scan will be considered meaningful differences in regards to the participant's background pulmonary status. In such an event, the patient will be discontinued from the study and will proceed to complete early discontinuation assessments and procedures.
- Patients on background MMF at study entry who need either (1) to switch to another background SSc-ILD medication, or (2) to begin additional treatment with another background SSc-ILD medication:
 - A decline of FVC by $\geq 15\%$ predicted or a decline of DLCO by $\geq 15\%$ predicted observed during the study that is sustained 4 weeks, or a decline of FVC itself to $<45\%$ predicted or decline of DLCO itself to $<40\%$ predicted observed during the study and if not explained by alternative etiology other than worsening scleroderma-related ILD as confirmed by HRCT chest scan will be considered meaningful differences in regards to the participant's background pulmonary status. In such an event, background MMF may not be switched to another agent in the study nor is the addition of other background medication permitted in the study; if this is necessary, the patient will be discontinued from the study and will proceed to complete early discontinuation assessments and procedures.
- Need for a prohibited medication
- Pregnancy
- Organ, stem cell, or bone marrow transplant
- At the discretion of the investigator

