For participants taking no background SSc-ILD medication at study entry who need to begin a SSc-ILD medication and participants on background MMF at study entry who need either (1) to switch to another background SSc-ILD medication, or (2) to begin additional treatment with another background SSc-ILD medication, the new SSc-ILD medication will be prescribed as routine clinical care and will not be provided as part of the study.

Participants who prematurely and permanently discontinue ixazomib study treatment will return to the clinic as soon as possible after the last dose of ixazomib and not later than 10 days after that dose to complete early discontinuation assessments and procedures as planned for study day 168 (week 24) office visit (see 18.3.10).

Participants who prematurely and permanently discontinue ixazomib study treatment will

again return to the clinic 28-35 days after completing the study early discontinuation assessments and procedures visit to complete early discontinuation assessments and procedures as planned for study post-treatment follow-up day 196-203 (week 28-29) office visit (see 18.3.11).

Any patient who prematurely and permanently discontinues ixazomib study treatment will be discontinued from the study and will be encouraged to continue post-discontinuation monitoring if eligible to do so.

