15.1.5 Final Post-Discontinuation Visit

Regardless of the number of post-discontinuation visits needed every 28 day ± 4 days following the date of completion of the early discontinuation assessments and procedures as planned for study day 168 (week 24), the final post-discontinuation visit will occur at a time point between what would have been study day visit 168 and study day 196-203 follow-up office visit should the participant have not prematurely discontinued ixazomib study medication. The final post-discontinuation visit will include following assessments and procedures:

1. Directed medical history including review of AEs/SAEs and concomitant medications that have been taken since the preceding visit.
2. Physical examination, including vital signs (blood pressure, heart rate, and respiratory rate) and body weight (in kilograms)
3. If participant is taking background MMF, confirm dose and timing of dosing.
4. mRSS
5. UCLA SCTC GIT 2.0 questionnaire
6. Disease-status scales:
 - a. Mahler TDI
 - b. SHAQ
 - c. PtGA

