24.2 Hypothesis Testing

No formal hypothesis testing will be done.

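### No rule brings participants removed for lung decline into the week-24 efficacy summary at their week-24 status, and the separate analysis of their later data measures change from a point after the decline

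*Combined protocol and SAP*

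**What the plan says.** The trial is small and descriptive. Section 7.1: "Planned enrollment will be 12 patients". Section 7.2 adds that "the study will include 6 study participants taking a stable oral dose of MMF", the other 6 taking no SSc-ILD treatment. On inference, section 24.2 says "No formal hypothesis testing will be done".

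**Removal.** Section 15.0 lists lung decline among the reasons for leaving drug and study: a fall in FVC or DLCO of at least 15% predicted "observed during the study that is sustained 4 weeks", or FVC below 45% or DLCO below 40% predicted, when worsening ILD is the explanation and HRCT confirms it. In the group without background medication this leads directly to removal. In the mycophenolate (MMF) group it does so only if a switch or an added agent is needed.

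**Collection after removal.** Within 10 days of the last dose the participant returns to "complete early discontinuation assessments and procedures as planned for study day 168 (week 24) office visit". Section 15.1.1 then encourages, but does not require, continued monitoring; lung-decline stops are on its list. Visits are every 28 days, and section 15.1.5 says "the final post-discontinuation visit will occur at a time point between what would have been study day visit 168 and study day 196-203". That final visit includes mRSS, complete pulmonary function tests, the disease-status scales, the physician global and HRCT.

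**Analysis.** For the individual measures, section 24.6.2 says "Analysis of these additional efficacy assessments will be based on the safety population". Its day-168 summaries of mRSS, FVC, DLCO, TLC and the scales use no imputation. That statement is not made for HRCT, nor for ACR CRISS in 24.6.1. Under section 24.8, participants who stop and "continue monitoring with post-discontinuation visits will be used for the analysis of" post-discontinuation efficacy. Section 24.8.2 takes changes in mRSS, FVC, DLCO, TLC and the scales from the early-discontinuation visit and does not list HRCT. The extension counterpart, 25.5.4.2, takes mRSS change from baseline and lung-function change from screening, and it does list HRCT.

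**The concern.** Removal is triggered by FVC and DLCO, which are themselves week-24 outcomes, so a missing week-24 value can be a consequence of the outcome. Without imputation, the row then describes participants who did not worsen enough to be removed. Naming the safety population does not change this, because a member with no day-168 value adds nothing to the row.

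The post-discontinuation analysis could restore the missing information, but its reference point comes after the fall. A reader of the results could then see a stable week-24 mean and a stable post-discontinuation change, with the decline in neither. Section 5.0 says the study may inform the design of later trials, so this matters even without a test.

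**Working it through.** The plan states no alpha, power, effect size, SD or dropout rate, so there is no figure of its own to reproduce. The check covers availability of the data, where each value goes, and size.

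**1. Is a value near week 24 obtainable?** The window from day 168 to day 203 spans 203 - 168 + 1 = 36 days, longer than the 28-day visit interval. Running every last-dose day from 1 to 155, with the early-discontinuation visit 0 to 10 days later and nominal 28-day visits after it, at least one visit always falls in the window. So the value can be obtained for each removed participant who accepts monitoring.

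**2. Where does each value go?**

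| Value from a removed participant | Use in the plan | Change measured from |
|---|---|---|
| FVC, DLCO at visits before removal | 24.6.2, earlier weeks | screening |
| Early-discontinuation visit | starting point in 24.8.2; use in the week-24 row not stated | not stated |
| Final visit: mRSS, FVC, DLCO, TLC, scales | 24.8.2 | early-discontinuation visit |
| Final visit: CRISS | 24.8.1 | baseline (Step 2) |
| Final visit: HRCT | not listed in 24.8 | none |
| Extension final visit: mRSS, lung function, HRCT | 25.5.4.2 | baseline or screening (HRCT also from week 24) |

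Invented example: FVC 70% at screening, 55% at early discontinuation, 55% at the final visit. The change in 24.8.2 is 55 - 55 = 0. From screening it is 55 - 70 = -15.

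**3. Size.** Let n be the group size, k the number removed, m the mean change of those remaining and d the change of those removed. The mean over everyone is ((n - k)m + kd)/n; the mean of those remaining is m. With m = 0 and d = -15 points (assumed, and assumed to persist):

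- one of 6: (5 x 0 - 15)/6 = -2.5
- one of 12: (11 x 0 - 15)/12 = -1.25
- two of 6: (4 x 0 - 30)/6 = -5.0

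For one of 6, final-visit falls of 1 to 20 points give -0.17 to -3.33. If 15% were read as relative, the fall at baselines of 45, 60 and 80 would be 6.75, 9 and 12 points; 9 points gives -9/6 = -1.5.

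**4. How often might it arise?** The chance of at least one removal is 1 - (1 - p)^n. At assumed removal rates p of 5%, 10% and 20%, this is 46%, 72% and 93% for n = 12, and 26%, 47% and 74% for n = 6.

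**5. CRISS.** Section 17.3.6 classes a participant with a Step 1 event as not improved. With baseline FVC at or below 100% predicted, a 15-point fall is at least 15% in relative terms (15/100 = 15%; 15/60 = 25%), so it reaches the Step 1 FVC threshold, subject to confirmation. Yet 24.6.1 tabulates Step 1 at scheduled study days and 24.8.1 tabulates it separately after stopping. Neither says whether the event carries to week 24.

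**The case against.** A reader might infer that the plan excludes worsening participants from the week-24 result. No sentence does so. They stay in the safety population, and the early-discontinuation visit includes the day-168 procedures. If that visit fills the week-24 row, the decline enters, and the contrast between 0 and -2.5 disappears when the fall is unchanged. This stands: what can be shown is a gap in the rules. But that reading would put a value from some other week in the week-24 row, and the final-visit value would still be unused there.

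Other limits also stand:

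- The final-visit data are not all assured. Monitoring is voluntary; pregnancy, transplant and the participant's own withdrawal are not on the 15.1.1 list; and the follow-up visit in 18.3.11 has no lung function or skin score.
- Absence of imputation is not stated for CRISS or HRCT, so loss of CRISS failures from the week-24 table is possible but not established.
- Earlier-week FVC and DLCO, disposition, and CRISS after stopping are all reported.
- Keeping off-drug values apart is a legitimate on-treatment summary.

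It is also tempting to set -2.5 beside the 2.53% difference that section 3.0 cites for cyclophosphamide. The two are not comparable. One is a between-group difference at 1 year in a controlled trial; the other is an assumed within-group shift at 24 weeks. One omitted fall of equal size in each group would leave the difference between groups unchanged.

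**Conclusion.** The point holds as a gap in the analysis rules. On the plain reading, the decline that led to removal is in neither the week-24 row nor the 24.8.2 change. The main-study and extension sections use different reference points, and the HRCT collected at the main-study final visit has no planned analysis.

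The possible effect is a favourable shift of about 2.5 FVC points in a group of 6, or 1.25 in all 12, for one removal. This rests on an assumed persisting 15-point fall, zero mean change in the others, and the early-discontinuation visit not being used at week 24. The documents give no removal rate. Safety is the primary objective and no test is planned, so no error rate is affected. The changes are still worth making before the summaries are produced.

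**What to change.** 1. In 24.6.1 and 24.6.2, beside the on-treatment summary, add a descriptive week-24 summary of all dosed participants. Those who stopped and accepted monitoring contribute the final post-discontinuation visit. State the window (day 168 to 203), label values off drug or on a new ILD medication, and show the number missing and the reasons for stopping. Do the same for week 48 in 25.5.2, counting participants who never entered the extension as missing.
2. In 24.8.2, report change from screening for lung function and from baseline for the other measures, in line with 25.5.4.2.
3. File early-discontinuation visits under their actual study week.
4. State that a CRISS Step 1 event counts as not improved at week 24 even if the participant has stopped.
5. Add the HRCT severity score and its change from baseline at the final post-discontinuation visit to 24.8.2.

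The cost is SAP wording and some extra descriptive rows, with no new visits or procedures and no change to any clinical rule. The drawback is that the added summary mixes on-drug values with values off drug or on another ILD medication, and participants who decline monitoring remain missing.
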